## PARTICIPANT MANAGEMENT

### 7.0 Inclusion and Exclusion Criteria\*

#### 6.1 Eligibility Criteria:

##### Inclusion Criteria

- T1D Diagnosis
- 16-19 years old
- 11th-12th graders
- Access to smartphone/laptop
- English-speaking (The Diabetes Link resources are only available in English)

#### 6.2 Vulnerable Populations: *Check any vulnerable populations that are being targeted for enrollment into the study: (Members of the following populations may not be included as participants in the research unless selected here.)*

 Children/Minors (under 7 years of age)	 Adults with impaired decision-making capacity
 Children/Minors (7-17 years of age)	 CM Employees
 Neonates (infants less than 30 days old)	 CM Students/Residents/ Fellows
 Neonates of Uncertain Viability (infants less than 30 days old)	 Economically or Educationally Disadvantaged Persons
 Non-Viable Neonates (infants less than 30 days old)	 Prisoners
 Wards of the State	
 Fetuses	
 Pregnant Women	

This study will include children (<18 Y.O.), who are a vulnerable population. We will collect data from the child's electronic health record and REDCap surveys. Many of the procedures required to collect these data are aspects of routine diabetes care for children and thus the risk for coercion/harm in participation is low. Parents will provide verbal permission for their child's participation.

### 8.0 Local Number of Participants

#### 7.1 *Indicate the total number of participants or charts to be enrolled locally as well as the accrual goal. If the study includes multiple groups or cohorts, be sure to describe the number of participants required for each*

**SHORT TITLE:**

*cohort. If one of the groups includes a chart review, each chart is considered a participant and needs to be reflected in the numbers below.*

**7.2**

	Prescreening	TID: 17-19 years old	
Enrollment Goal: Number of participants to be enrolled = the number of participants to be consented or to be screened for chart reviews.	65	20	

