## STUDY INFORMATION

### 1.0 Study Summary\*

Study Title	An Investigation of the Diabetes Link Discord Platform
Study Design	Single site, pilot, longitudinal
Primary Objective	To examine the feasibility and acceptability of the Diabetes Link's online social platform Discord among youth with diabetes as it relates to peer support, diabetes management, and usability.
Secondary Objective	To examine the efficacy/magnitude of the effect of the Discord group on treatment adherence among youth with diabetes.
Research Intervention(s)	Participants will join the Children's Mercy Discord group led by the nonprofit Diabetes Link. Participants will participate in live video gatherings, as well as posted chats/prompts, and will answer a few qualitative questions at the end of their participation. Discord user metrics--both quantitative and qualitative (deidentified transcripts/audio recordings)--and health record metrics will be analyzed in addition to the end survey.
IND/IDE #	N/A
Study Population	T1D patients in 11 th and 12 th grade (ages 16-19) who have access to a smartphone/laptop and speak English
Sample Size	Sample size for app use: 20 11 th /12 th graders
Study Duration for Individual Participants	Users will use Discord for 3 months.
Study Specific Abbreviations/Definitions	DL = Diabetes Link Nonprofit Organization T1D= type one diabetes T2D= type two diabetes Children's Mercy Hospital Kansas City (CMH) Mobile Application (app or apps) Children's Mercy- Kansas City (CMKC)

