**8.3 Recruitment of Potential Participants:**

Patients will be prescreened to see if they meet enrollment criteria by a member of the research team. Patients who appear to meet criteria may be contacted by telephone or approached during a standard of care visit by a study team member and informed about this study. They may also learn of the study through the intake form, Find A Study page, or the study flyer. The flyer can be posted on the Diabetes Clinic intake form that families complete before appointments or in clinic spaces. The flyer and Study Information Sheet can be posted on the hospital's Find a Study page. Patients and their parent/legal guardian will be given information about the study and they will determine if they wish to participate. Once the potential participant has talked to a study coordinator about the study, the inclusion/exclusion survey will be shared with the participant via REDCap for completion.

If Recruitment takes place via telephone CM research policy will be followed.

Prescreening may involve either a review of clinic schedules or a report generated by IT that will involve a review of the electronic medical record (EMR) system to generate a list of potentially eligible participants.

Data will be stored in both REDCap and the CM Azure Cloud. All electronic survey data will be stored on a CMH shared drive folder and REDCap with access given only to the research personnel listed on this study.

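### Does the 17-19 age label on the Section 8.0 enrolment table, against 16-19 elsewhere, require a change to the plan?

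*Protocol*

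**What the plan says.** The protocol states the age of the cohort in three places.

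- Section 1.0 (Study Summary) describes the population as patients with type 1 diabetes in 11th or 12th "grade (ages 16-19) who have access to a smartphone/laptop and speak English". It gives the size as "Sample size for app use: 20", followed by the same two school grades.
- Section 7.0 (Inclusion Criteria) lists "16-19 years old", together with the diagnosis, the two grades, access to a device and English.
- Section 8.0 (item 7.2) has a table with two columns of numbers. The first, for prescreening, carries 65 and no age. The second carries 20 and is headed "TID: 17-19 years old".

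Two further places bear on the point. Section 7.0, item 6.2, says "This study will include children (<18 Y.O.), who are a vulnerable population". Section 9.0, item 8.3, says "Patients will be prescreened to see if they meet enrollment criteria by a member of the research team", and adds that, after a conversation with a coordinator, "the inclusion/exclusion survey will be shared with the participant via REDCap for completion".

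**The concern.** An age limit is part of the definition of the study population, and here one cohort carries two of them. A reader who turned only to Section 8.0 would take the study to be closed to 16-year-olds, whom Section 7.0 admits.

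If staff screened on the narrower range, two things would follow. The 20 participants would come from a smaller pool than the summary describes. The feasibility measures named in the Aim 1 hypothesis, such as the enrolment and refusal rates, would also have a different denominator, because 16-year-olds would never be approached. In a pilot whose main purpose is feasibility, that would be worth knowing. It is therefore right to ask whether the label could steer who is enrolled.

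**Working it through.** No formula applies. The protocol text at hand gives no power or precision inputs from which 20 could be derived, so the check is a comparison of the statements.

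| Place in the protocol | Age range | Number |
|---|---|---|
| Section 1.0, population and sample size | 16-19 | 20 |
| Section 7.0, inclusion criteria | 16-19 | none given |
| Section 8.0, prescreening column | none given | 65 |
| Section 8.0, participant column | 17-19 | 20 |

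**Size of the mismatch.** The lower limits differ by 17 - 16 = 1 year, and the upper limit is 19 throughout. The counts agree: 20 - 20 = 0.

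**Could the heading mark a subgroup?** The template text in Section 8.0 asks for a number per cohort if there are several. The table has one participant column, and its 20 is the whole sample size of Section 1.0. If those 20 were only a 17-19 subgroup, no place would be left for a 16-year-old, who is eligible under Section 7.0. The heading therefore labels the full cohort, with a different lower limit.

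**Could it be older text left behind, or a reading fault?** The revision history has column headings and no entries, so it shows nothing either way. The first word of the heading has a letter I where a figure 1 belongs, which may be a typing or scanning error, but the age digits are legible. The mismatch has to be taken as it stands.

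**Does the label act on anything?**

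1. *Eligibility.* The age criterion is listed under the inclusion criteria. The row instruction in the Section 8.0 table asks only for a number of participants.
2. *Screening.* Item 8.3 ties prescreening to the enrolment criteria and follows it with an inclusion/exclusion survey. It does not refer to the Section 8.0 table.
3. *Permission.* Ages 16 and 17 both fall in the ticked category of minors aged 7 to 17, for whom item 6.2 requires parental permission. That category is in use whichever lower limit is taken. For the same reason, the statement that children are included does not show which limit was meant.
4. *Sample size and analysis.* The target is 20 under either range. The text at hand describes no comparison group and no analysis by age that could be disturbed.

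**The case for a change.** The strongest case for a change is that Section 8.0 is where the protocol says how many people of which kind will be enrolled. Read literally, it allots nobody to age 16. Item 8.3 allows a list of candidates to be produced by an IT report from the medical record. If whoever specified that report took the age from Section 8.0, eligible 16-year-olds would be missed. The correction is one table cell, so there seems little reason not to require it.

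Part of this stands. The two ranges do contradict each other, and no reading of the available text removes the conflict. The rest is conjecture. Nothing in the protocol makes the table an allocation by age or says that it feeds the report. The report's stated purpose is to list potentially eligible patients, which points to the inclusion criteria. A wrongly specified list would also not be the only way in, since item 8.3 names clinic visits, the intake form, a flyer and a web page as further routes. A low cost of correction does not turn a labelling slip into a defect of the plan.

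Three limits on the reassurance should be stated. Item 8.3 speaks of enrolment criteria without naming Section 7.0, so the link is a natural reading and not an explicit rule. The text at hand passes from Section 9.0 to Section 31.0, so the absence of a 17-19 subgroup is established only for what can be read. Two statements against one make 16-19 the likely intention, not a certain one.

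**Conclusion.** The inconsistency is genuine but clerical, and no change to the plan is called for. Its size is one year in the lower age limit of one column heading. The enrolment target of 20 is unchanged, and the summary and the inclusion criteria agree with each other. How many participants would be aged 16 cannot be given, because the available text contains no expected age distribution. The figure is not needed, since the label excludes nobody.

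The conclusion rests on two assumptions: that staff screen against the inclusion criteria, as item 8.3 is most naturally read, and that no section outside the available text defines a separate 17-19 cohort. Given these, a reader who meets both ranges will take the eligibility section as governing. The study will then enrol the same people and report the same results whether or not the heading is tidied.

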**9.0 Identification and Recruitment of Potential Participants\***

**8.1 Identification of Potential Participants:**

How will participants be identified? (Check all that apply)

- Chart reviews
- By their treating physician who will then provide the study team's contact information to the potential participant/family
- By their treating physician who will obtain patient/family permission to share contact information with the study team
- Self-refer in response to IRB approved advertisements or websites
- Through Cerner or other CM sources (e.g. databases, billing records, pathology reports, admission logs, etc.) May involve access of records by individuals not involved in the patient's care.
- List of candidates provided through the Data Report Request Form
- Registry of individuals interested in research opportunities
- Past participant list
- Participants will roll-over from another research study: Study #
- Other:

**8.2 Pre-Screening prior to HIPAA Authorization**

**SHORT TITLE:**

Will any of the identification methods checked above involve access to Protected Health Information (PHI) prior to obtaining HIPAA Authorization?

Yes

No

- *If yes, a "Partial Waiver of HIPAA Authorization" is required. Be sure to make this selection in the "HIPAA & Confidentiality" section below and complete [Addendum E: Waiver/Alteration of HIPAA Authorization](#)*

**8.3 Recruitment of Potential Participants:**

Patients will be prescreened to see if they meet enrollment criteria by a member of the research team. Patients who appear to meet criteria may be contacted by telephone or approached during a standard of care visit by a study team member and informed about this study. They may also learn of the study through the intake form, Find A Study page, or the study flyer. The flyer can be posted on the Diabetes Clinic intake form that families complete before appointments or in clinic spaces. The flyer and Study Information Sheet can be posted on the hospital's Find a Study page. Patients and their parent/legal guardian will be given information about the study and they will determine if they wish to participate. Once the potential participant has talked to a study coordinator about the study, the inclusion/exclusion survey will be shared with the participant via REDCap for completion.

If Recruitment takes place via telephone CM research policy will be followed.

Prescreening may involve either a review of clinic schedules or a report generated by IT that will involve a review of the electronic medical record (EMR) system to generate a list of potentially eligible participants.

Data will be stored in both REDCap and the CM Azure Cloud. All electronic survey data will be stored on a CMH shared drive folder and REDCap with access given only to the research personnel listed on this study.

**31.0 Provisions to Monitor the Data to Ensure the Safety of Participants**

**SHORT TITLE:**

See Data Management above. This study presents to more than minimal risk for participants.

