## ***Addendum A: Waiver of Documentation of Permission/Consent***

**Regulatory Criteria:** *To qualify for a waiver of documentation of parental permission or adult consent, the study must fit into at least one of the three scenarios below. Indicate which scenario(s) applies.*

**The only record linking the participant and the research would be the permission/consent form and the principal risk is potential harm resulting from a breach of confidentiality.** Each parent/LAR or adult participant will be asked whether they want documentation linking the participant with the research, and the parent/LAR's or adult participant's wishes will govern.

OR

**The research presents no more than minimal risk of harm to participants and involves no procedures for which written parental permission or adult consent is normally required outside of the research context.**

OR

**The parent(s)/LAR or adult participants are members of a distinct cultural group or community in which signing forms is not the norm,** the research presents no more than minimal risk of harm to participants and an appropriate alternative mechanism for documenting that informed parental/LAR permission or adult consent was obtained will be provided. Describe the alternative mechanism provided:

SHORT TITLE:

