**SHORT TITLE:**

The research cannot practicably be conducted without the waiver/alteration, i.e. explain why a signature for HIPAA Authorization cannot be obtained.
	
Partial HIPAA Waiver for Screening: It would not be practical to obtain HIPAA authorization for every person screened as they will not know who meets the inclusion criteria until the records are accessed
 
Alteration for HIPAA Authorization: The consent process will take place remotely. The study team will not have face to face interaction with participants for the study.

The research cannot practicably be conducted without access to and use of the PHI, i.e. explain why access to PHI is needed for this study.
	
Partial HIPAA Waiver for Screening: PHI must be accessed in order to determine eligible patients for recruitment.
 
Alteration for HIPAA Authorization: All collected data is needed to meet the study aims.

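### Does Section 31.0 classify the study as more than minimal risk, and so undercut verbal parental permission and the HIPAA alteration?

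*Protocol*

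**What the plan says.** Four places in the protocol bear on this.

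- **Section 31.0** (safety monitoring) refers the reader back to Data Management and adds "This study presents to more than minimal risk for participants".
- **Section 6.2** (Vulnerable Populations) ticks minors aged 7 to 17. It notes that many of the procedures are part of routine diabetes care and concludes "thus the risk for coercion/harm in participation is low". It then says "Parents will provide verbal permission for their child's participation".
- **Addendum A** lists three alternative grounds for doing without signed permission. The second begins "The research presents no more than minimal risk of harm to participants", and the third carries the same risk condition. The first has no risk condition, but requires that the consent form be the only record tying the participant to the research.
- **Addendum E** supports the alteration of HIPAA authorization by saying that consent is taken remotely and that "The study team will not have face to face interaction with participants for the study". **Section 8.3** says that patients who seem eligible "may be contacted by telephone or approached during a standard of care visit by a study team member" and told about the study.

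**The concern.** Read as printed, the safety section contradicts the low-risk statement in Section 6.2, and the contradiction would carry through to consent. The first ground in Addendum A does not fit a study that collects health-record and REDCap data on each child and keeps a recruitment log. That leaves the two grounds that require minimal risk. If the study were above minimal risk, verbal permission for the minors would have no visible basis, and one could fear that their data would be challenged later.

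The HIPAA point has the same shape. A justification that rests on never meeting participants looks unsound if study staff may approach them in clinic.

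At stake would be the standing of every participant under 18 in a group of 20 and, at one remove, the precision of the pilot's estimates.

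**Working it through.** The protocol gives no figure to reproduce here, so the check is mainly a comparison of texts.

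**1. The sentence in Section 31.0.** It is not grammatical as it stands. Two one-word repairs are possible.

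- *Replace* to *with* no. One letter changes, and the result is the phrase that Addendum A itself uses. It agrees with Section 6.2. It also explains why the section gives only a cross-reference: a low-risk study needs little more.
- *Delete* to. The result is grammatical, but it asserts a risk level that nothing else in the text at hand supports. It would also sit oddly beside a bare cross-reference.

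Addendum E has also been completed on the footing that the use of health information poses no more than minimal risk to privacy. That is a narrower statement, but it points the same way. So do the study activities, which are live video events, posts, a short survey and record review. The first repair is far more likely. Stray characters occur elsewhere in the text (T1D appears as TID in the enrolment table at 7.2), so a misread character is also possible.

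**2. The link to Addendum A.** No tick mark is visible there, so the ground relied on is inferred by ruling out the first. If the second ground was selected, the protocol already asserts minimal risk, and Section 31.0 is plainly the slip.

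**3. Face-to-face contact.** Addendum E answers the question of why a signature cannot be obtained, and its first reason is remote consent. Section 8.3 describes an optional step before enrolment, by telephone or at a visit that would take place anyway, in which patients are informed. It does not place consent or authorization in clinic. The two fit together as clinic or telephone approach followed by remote consent. Only the unqualified second sentence in Addendum E goes too far.

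**4. Monitoring.** Section 31.0 points to Data Management. Sections 10.0 to 30.0, which include risks, consent, adverse events and data management, are in the table of contents but not in the text at hand. Nothing can be concluded about how much monitoring is planned.

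**5. Precision, if participants were lost.** Suppose 4 to 6 of the 20 were excluded for invalid permission. The 95% half-width for a paired mean change, in SD units, is t(0.975, n−1)/√n:

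| n | half-width (SD) |
|---|---|
| 20 | 0.468 |
| 16 | 0.533 |
| 14 | 0.577 |

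The arithmetic is right, but the loss of 4 to 6 is an assumption with no source in the protocol. The age mix is not given either. Eligibility is 16 to 19 years, while the table at 7.2 labels the enrolled group 17 to 19, so the share under 18 is unknown. A wording slip excludes nobody, so the applicable row is n = 20.

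**The case for a change.** The strongest case for acting is that this is the current text, that the section is one a monitor or auditor would consult, and that one wrong letter reverses the risk classification in a study enrolling minors. A probable slip is still wrong on the page, and a restatement of the risk level in another section would not correct it. Likewise, Addendum E denies in-person contact without exception, and an approach in clinic is in-person contact, however brief.

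All of that stands as a point of drafting: both sentences are worded badly and should agree with the review board's determination and with Section 8.3. What does not stand is the step from drafting to consequence. Nothing visible suggests that the study was judged above minimal risk, that consent is taken in a way the protocol does not allow, or that data would be lost.

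**Conclusion.** No change to the plan follows. The risk sentence is a clerical slip whose intended meaning is clear from Section 6.2. The Addendum E sentence is broader than it needs to be, but it is compatible with Section 8.3 once read as describing consent and authorization. Both are wording matters for the next routine revision. The effect on the enrolment goal, outcomes, analysis, bias and precision is zero.

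This rests on two assumptions: that the review board determined the study to be minimal risk, and that the sections not at hand do not say otherwise. If the board had determined a higher risk, the consent route and the safety section would have to be reconciled with that decision. That would be a question for the board, and the documents give no sign of it.

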**STUDY MANAGEMENT**

**32.0 Setting & Locations\*** **N/A**

**33.0 Multi-Site Research** **N/A**

**34.0 International Research** **N/A**

SHORT TITLE:

## ***Addendum A: Waiver of Documentation of Permission/Consent***

**Regulatory Criteria:** *To qualify for a waiver of documentation of parental permission or adult consent, the study must fit into at least one of the three scenarios below. Indicate which scenario(s) applies.*

**The only record linking the participant and the research would be the permission/consent form and the principal risk is potential harm resulting from a breach of confidentiality.** Each parent/LAR or adult participant will be asked whether they want documentation linking the participant with the research, and the parent/LAR's or adult participant's wishes will govern.

OR

**The research presents no more than minimal risk of harm to participants and involves no procedures for which written parental permission or adult consent is normally required outside of the research context.**

OR

**The parent(s)/LAR or adult participants are members of a distinct cultural group or community in which signing forms is not the norm,** the research presents no more than minimal risk of harm to participants and an appropriate alternative mechanism for documenting that informed parental/LAR permission or adult consent was obtained will be provided. Describe the alternative mechanism provided:

SHORT TITLE:

